### 3.2.1. Use in Specific Populations

**Pregnancy:** Xarelto® dosing in pregnancy has not been studied. The limited available data on Xarelto® in pregnant women are insufficient to inform a drug-associated risk of adverse developmental outcomes. There is a risk of pregnancy-related hemorrhage due to the potential for obstetric hemorrhage and/or emergent delivery. Rivaroxaban should only be used if benefits outweigh risk. Pregnancy is a known risk factor for VTE but not for COVID-19. This study will exclude pregnant women.

**Lactation:** There is insufficient data to determine the effect of rivaroxaban on the breastfed child or on milk production. This study will exclude lactating women.

### 3.2.2. Rationale for the Use of Rivaroxaban for Treatment of Mild COVID-19

COVID-19 progression requiring hospitalization generally occurs from the second week of illness and is characterized by intense systemic inflammation and hypercoagulability. People who present with mild COVID-19 during the first week are likely transitioning from the active viral replication phase to the inflammatory phase of the disease [Siddiqi 2020]. This offers a unique opportunity to intervene early and prevent further progression of disease by evaluating a thromboprophylactic drug, rivaroxaban, in people at risk for COVID-19 progression.

There is precedent for the use of approved drugs with a well-characterized and favorable safety profile to be considered for treatment of COVID-19. For example, remdesivir, although not approved as a treatment for COVID-19, has received FDA Emergency Use Authorization for hospitalized COVID-19 patients [FDA 2020].

#### 3.2.2.1. Rationale for a Limit of 7 Days of Mild COVID-19 Symptoms Prior to Randomization

The incubation period from exposure to early manifestations of COVID-19 ranges from 2 to 14 days. During the first 3 days of illness, COVID-19 symptoms may be non-specific and include

cough, fever, headache, lethargy, and/or diarrhea. During the next 3-5 days some patients develop worsened symptoms but some patients may show signs of recovery. The second week of illness, Days 8-12, is when progression to signs and symptoms indicative of a hyperinflammatory phase is more likely to occur. These may include dyspnea, abnormal imaging of the lungs, respiratory failure, ARDS, and/or cytokine storm syndrome. In a large series of 410 patients with COVID-19 hospitalized in Italy [Ciceri 2020], the median (IQR) days from COVID-19 symptoms onset to hospitalization was 8 days (5-11) days. Approximately 50% of these patients were aged >65 years and approximately 60% had one or more comorbidities.

The primary endpoint of this study is the time to progression of COVID-19 from Scale 2 to Scale 3 or higher – a situation that would likely require hospitalization of the participant. The data from the cited Italian study can inform the choice of the interval between onset of symptoms and the expected time of initiation of study drug therapy. Because the interval from onset of symptoms to randomization should be no more than 7 days resulting in the worst-case scenario of an interval of around 9 days from onset of symptoms to first dose of study treatment (assuming two days for shipment of IP and supplies). Nine days falls within the IQR reported by Ciceri, et al [Ciceri 2020].

### **3.2.3. Benefit/Risk Assessment**

The elderly ( $\geq 65$  years of age) and those with medical comorbidities (e.g., cardiopulmonary disease, diabetes mellitus) or obesity are at high risk of poor outcomes from COVID-19 [Chen 2020, Huang 2020, Richardson 2020, Zhu 2020]. In a large case series of COVID-19 patients in New York City, the risks for hospitalization were 10-times and 40-times higher in people 65 to 74 years old and over 75 years old compared to those younger than 45 years old. People with high BMI and comorbidities are 2 to 5 times more likely to be hospitalized compared to those without risk. Similarly, mortality rates are higher in people with these risk factors [Petrilli 2020].

It is estimated that 20% to 30% of people with risk factors will progress to moderate or severe COVID-19 [Williams 2020]. The benefit-to-risk ratio for testing treatment is favorable in this population.

#### **3.2.3.1. Benefit/Risk Assessment of Rivaroxaban**

Without any approved treatment for outpatients with COVID-19, there is a favorable benefit-risk ratio for using rivaroxaban in the target population at increased risk for progressing to moderate and severe COVID-19.

Rivaroxaban is an approved drug with a well-characterized and favorable safety profile.

The dose selected for this study (10mg/day) is the same as the licensed prophylactic dose for VTE in acutely ill patients and fits the purpose of preventing thromboembolic events in people with acute COVID-19 illness. This study will exclude people who may be at increased risk for adverse events or drug interactions due to rivaroxaban as well as those with severe renal and liver impairment, and pregnant and breastfeeding women.

### **3.2.4. Rivaroxaban Mechanism of Action**

Rivaroxaban is a selective inhibitor of factor Xa, the activated form of coagulation factor X. It does not require a cofactor (such as anti-thrombin III) for activity. Rivaroxaban inhibits free factor Xa and prothrombinase activity. Rivaroxaban has no direct effect on platelet aggregation, but indirectly inhibits platelet aggregation induced by thrombin. By inhibiting factor Xa, rivaroxaban decreases thrombin generation.

### **3.2.5. Rivaroxaban Pharmacokinetics**

#### ***Absorption***

The absolute bioavailability of rivaroxaban is dose-dependent. For the 2.5 mg and 10 mg dose, it is estimated to be 80% to 100% and is not affected by food. Rivaroxaban 2.5 mg and 10 mg tablets can be taken with or without food. For the 20 mg dose in the fasted state, the absolute bioavailability is approximately 66%.

Coadministration of rivaroxaban with food increases the bioavailability of the 20 mg dose (mean area under the curve (AUC) and maximum concentrations (Cmax), increasing by 39% and 76% respectively, with food).

The Cmax of rivaroxaban appears 2 to 4 hours after tablet intake.

#### ***Distribution***

Plasma protein binding of rivaroxaban in human plasma is approximately 92% to 95%, with albumin being the main binding component. The steady-state volume of distribution in healthy subjects is approximately 50 L.

#### ***Metabolism***

Approximately 51% of an orally administered [C]-rivaroxaban dose was recovered as inactive metabolites in urine (30%) and feces (21%). Oxidative degradation catalyzed by CYP3A4/5 and CYP2J2 and hydrolysis are the major sites of biotransformation. Unchanged rivaroxaban was the predominant moiety in plasma with no major or active circulating metabolites.

#### ***Excretion***

In a Phase 1 study, following the administration of [C]-rivaroxaban, approximately one third (36%) was recovered as unchanged drug in the urine and 7% was recovered as unchanged drug in feces. Unchanged drug is excreted into urine, mainly via active tubular secretion and to a lesser extent via glomerular filtration (approximate 5:1 ratio). Rivaroxaban is a substrate of the efflux transporter proteins, P-glycoprotein (P-gp) and ABCG2 (also abbreviated Bcrp). Rivaroxaban's affinity for influx transporter proteins is unknown.

Rivaroxaban is a low-clearance drug, with a systemic clearance of approximately 10 L/hr in healthy volunteers following intravenous administration. The terminal elimination half-life of rivaroxaban is 5 to 9 hours in healthy subjects aged 20 to 45 years, and 11 to 13 hours in the elder participants aged 60 to 76 years

Pharmacokinetics (PK) and pharmacodynamics (PD) of rivaroxaban were not influenced by gender, but by race (higher exposure in healthy Japanese) and severe renal and liver impairment (which are exclusion criteria in this study). Please refer to package insert for more information.

Refer to [Section 6.4](#) for dose modification and toxicity management.

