Appendix 1: Platform Core Protocol

## List of Abbreviations and Terms

Term	Definition
AE	Adverse Event
AESI	Adverse Event of Special Interest
AUC	Area Under the Curve
BMI	Body Mass Index
CI	Confidence Interval
Cmax	Maximum Concentration
COVID-19	Coronavirus Disease 2019
CRF/eCRF	(Electronic) Case Report Form
CRO	Contract research organization
DOAC	Direct Oral Anticoagulant
DVT	Deep Vein Thrombosis
Eligible	Qualified for enrollment into the study based upon adherence to inclusion/exclusion criteria
Gates MRI	Bill & Melinda Gates Medical Research Institute
GCP	Good Clinical Practices
IDMC	Independent Data Monitoring Committee
IEC	Independent Ethics Committee
IP	Investigational Product
IRB	Institutional Review Board
ITT	Intention to Treat
LRTI	Lower Respiratory Tract Infection
mITT	Modified Intention to Treat
Participant(s)	Term used throughout the protocol to denote the enrolled individual(s)
PD	Pharmacodynamic
PE	Pulmonary embolism
P-gp	P-glycoprotein
PK	Pharmacokinetic
PP	Per Protocol
SAE	Serious Adverse Event
SAP	Statistical Analysis Plan
SARS-CoV-2	Severe Acute Respiratory Syndrome Coronavirus 2
SoA	Schedule of Activities
US	United States
VTE	Venous Thromboembolism
WHO	World Health Organization

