### **5.5.2. Exclusion Criteria**

Participants are excluded from the study if any of the following criteria apply:

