#### **Medical Conditions or history**

1. Currently hospitalized or under immediate consideration for hospitalization at screening and Day 1
2. Have new onset shortness of breath or increased shortness of breath from pre-COVID-19 (for people with known COPD) at screening and Day 1
3. Hypoxemia (oxygen saturation<94% in ambient air or oxygen saturation below pre-COVID-19 oxygen saturation [if known] for people with known COPD) at Day 1
4. Require supplemental oxygen (new requirement or increase in requirement from pre-COVID-19 condition) at screening and Day 1
5. Have a history of (in the past 3 months) or current active pathological bleeding
6. Have a history of hemorrhagic stroke or intracranial hemorrhage
7. Have a recent severe head trauma within 30 days which includes concussion, skull fracture or hospitalization for head injury
8. Have known intracranial neoplasm, cerebral metastases, arteriovenous malformation or aneurysm
9. Have history of pregnancy-related hemorrhage
10. Have active gastroduodenal ulcer or other gastrointestinal bleeding diagnosed in the past 3 months
11. Currently are in a hemodynamically unstable state
12. Currently require thrombolysis or pulmonary embolectomy
13. Have history of severe hypersensitivity reaction to Xarelto®
14. Currently have a prosthetic heart valve
15. Have known diagnosis of triple positive antiphospholipid syndrome
16. Have known diagnosis of chronic kidney disease (stage IV or receiving dialysis)
17. Have a history of thrombocytopenia or known platelet count < 100,000 cells/mm^3
18. Have a history of bronchiectasis and pulmonary cavitation
19. Have active cancer (eg, receiving chemotherapy or treatment for complication of the active cancer)

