## **7. Discontinuation/Withdrawal Criteria and Study Completion**

### **7.1. Discontinuation of Study Intervention**

Study intervention will be discontinued for the following reasons:

- Hospitalization, if the in-patient provider decides continuation of study treatment is contraindicated.
- Requirement for prohibited concomitant medications or other contraindication to study product
- Occurrence of an AE requiring discontinuation of study intervention (i.e., severe hypersensitivity, major bleeding or clinically relevant non-major bleeding)
- Request by participant to terminate study intervention
- Clinical reasons believed to be life-threatening by the physician, even if not addressed in this protocol
- Pregnancy.

Participants who stop study intervention should continue study participation while off of the study intervention, with continued evaluations as per the SoA. The reason for study intervention discontinuation should be recorded.

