## **7.2. Withdrawal from the Study**

A participant may withdraw from the study at any time at the participant's request or may be withdrawn at any time for the following reasons:

- At the request of the primary care provider if being in the study is no longer in the best interest of the participant
- Participant is judged by the PI to be at significant risk of failing to comply with the provisions of the protocol as to cause harm to self or seriously interfere with the validity of the study results
- At the discretion of the IRB/IEC or government agencies as part of their duties, PI, or Sponsor.
- The participant progressed to moderate or severe COVID-19 (or worse) prior to initiation of IP dosing on Day 1

If the participant withdraws consent for disclosure of future information, the Sponsor may retain and continue to use any data collected before such withdrawal of consent.

Upon withdrawal from the study, the participant may request destruction of any biological samples taken and not tested, and the PI or designee must document this in the site study records.

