#### **8.1. Screening Process and Procedures**

The following procedures must occur  $\leq 5$  days prior to the Day 1 visit. All screening evaluations must be completed and reviewed to confirm that potential participants meet all eligibility criteria.

The PI/study staff will maintain a screening log to record details of all participants screened and to confirm eligibility or record reasons for screening failure, as applicable. This does not apply to any pre-screening procedures.

Procedures conducted as part of the participant's routine clinical management and obtained before signing the informed consent form may be utilized for screening purposes provided that the procedures met the protocol-specified criteria and were performed within the time frame defined in the SoA.

The study staff conducting the Screening visit will:

- Introduce themselves and their role to the participant, and confirm the identity of the participant.
- Confirm that the means of contact is adequate to conduct the contact/visit
- Obtain informed consent (refer to [Section 11.2](#) for details)
- Collect demographic information -age, sex, race and ethnicity and personal information including name and address
- Collect information in past and current medical conditions, including known pregnancy and/or lactation status
- Collect concomitant medication information (refer to [Section 6.10](#) for details).
- Collect documented positive SARS-CoV-2 diagnostic testing performed with a sample collected  $\leq 10$  days of screening. If no document is available, SARS-CoV-2 diagnostic testing will be performed at screening.
- Check inclusion and exclusion criteria.

Eligible participants who meet all criteria will be enrolled and randomized to a study group and will receive supplies and study IP, delivered to the participant at home, or if deemed necessary, it may be picked up at study site or other methods may be used as appropriate.

Eligible participants will receive the following:

- Study IP with dosing direction and storage information
- An oximeter and a thermometer, with user instructions
- Nasal test kit, with user instructions
- Personal protective equipment (face masks, shields and gloves).

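### Protocol Sections 3.2.3.1 and 3.2.5 say people with severe liver impairment are excluded, but the 26-item exclusion list in Section 5.5.2 has no hepatic criterion

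*Protocol*

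**What the plan says.** Two current sections of the protocol state the exclusion.

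- Section 3.2.5 (Excretion) says that the drug's pharmacokinetics and pharmacodynamics are influenced by "severe renal and liver impairment (which are exclusion criteria in this study").
- Section 3.2.3.1 (Benefit/Risk Assessment of Rivaroxaban) says the study will exclude people at increased risk of adverse events or drug interactions, "as well as those with severe renal and liver impairment, and pregnant and breastfeeding women".

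The operative list is in Section 5.5.2, which opens with "Participants are excluded from the study if any of the following criteria apply" and then gives items 1 to 26. Its renal item, criterion 16, reads "Have known diagnosis of chronic kidney disease (stage IV or receiving dialysis"). There is no hepatic item.

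The protocol makes that list decisive. The List of Abbreviations and Terms defines Eligible as "Qualified for enrollment into the study based upon adherence to inclusion/exclusion criteria", and Section 8.1 says "Eligible participants who meet all criteria will be enrolled and randomized to a study group".

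**The concern.** A safety exclusion that the protocol relies on in its benefit/risk argument does not appear where sites check eligibility. By the protocol's own account, severe liver impairment alters the behaviour of this anticoagulant. Staff working down Section 5.5 would find nothing that asks about the liver and no definition of severe to apply.

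Two things are at stake. One is the safety of any such person who is enrolled. The other is accurate reporting: a study report that repeats the background statements would describe an exclusion that no criterion put into effect. The statistical design is not involved.

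**Working it through.** This is a check of the text. The only arithmetic is a count.

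**Step 1: count the exclusion items in Section 5.5.2.**
- Medical conditions or history: items 1 to 19, so 19.
- Other: items 20 to 25, so 6.
- Medications: item 26, so 1.
- Total: 19 + 6 + 1 = 26, numbered without a break. A line lost in reading the PDF is therefore not a likely explanation.

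**Step 2: look for the liver.** None of the 26 items mentions the liver, hepatic disease, cirrhosis or liver tests: 0 of 26. The inclusion criteria in Section 5.5.1 carry no hepatic restriction either.

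**Step 3: match each group named in Section 3.2.3.1 to a criterion.**

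| Group named in Section 3.2.3.1 | Criterion in Section 5.5.2 |
|---|---|
| Severe renal impairment | 16 (threshold: known stage IV disease or dialysis) |
| Severe liver impairment | none |
| Pregnant women | 22 |
| Breastfeeding women | 23 |

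Three of the four groups were carried through. Section 3.2 also repeats the renal exclusion with its threshold, and has no hepatic counterpart.

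**Step 4: see whether another entry rule fills the gap.**
- The list has no general exclusion at the investigator's judgement.
- Criteria 5, 10 and 17 (pathological bleeding, ulcer or gastrointestinal bleeding, low platelets) would catch some people with severe liver disease, but not all.
- Inclusion criterion 2 accepts any chronic disease that the site investigator considers a high risk for severe COVID. Chronic liver disease could thus help a person to qualify.
- The Schedule of Activities (Table 1) contains no liver test.
- Section 3.2.5 sends the reader to Section 6.4 for dose modification, and Section 6.4 allows none.

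**Step 5: see whether rules that act after enrolment fill the gap.**
- Section 7.2 allows withdrawal "At the discretion of the IRB/IEC or government agencies as part of their duties, PI, or Sponsor". This is discretionary.
- Section 7.1 stops study drug for "Requirement for prohibited concomitant medications or other contraindication to study product". It governs stopping, not entry.
- Section 6.4 requires a question about bleeding at each visit and stops study drug for major or clinically relevant non-major bleeding. Section 6.6 pauses enrolment and dosing after one major bleed judged related. These limit harm after dosing has begun.

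None of the rules in Step 5 makes the person ineligible.

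**The case against.** The factual mismatch is hard to dispute. The case on the other side concerns its consequences, and much of that case stands.

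**Protocol deviation.** A reader might infer that a site could dose such a person with no protocol deviation. The documents do not support that. Section 3.2.3.1 is itself protocol text and is worded as a directive, so knowingly enrolling the person would contradict it even though Section 5.5.2 is silent. Whether the event would be logged as a deviation is unclear.

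**Contraindication clause.** A reader might also infer that the stopping rule in Section 7.1 could never apply, because the two contraindications listed in Section 3.2 are active pathological bleeding and severe hypersensitivity. Section 7.1 does not tie its wording to that list. A clinician could reasonably read it to cover a condition that the protocol says it excludes.

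**Other protections.** Section 3.2 says that use will follow the label guidance for patients not at high risk of bleeding. Together with the bleeding rules in Sections 6.4 and 6.6, this reduces the potential harm. It does not supply an entry criterion.

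**Unseen text.** Appendix 1, the platform core protocol, is not among the documents, so a hepatic rule there cannot be ruled out. It would not remove the inconsistency, because the Synopsis and Section 5.2 direct the reader to Section 5.5 and its criteria for eligibility. The amendment history cannot show whether a hepatic criterion was once present and then dropped, because itemised changes begin only after Version 4.

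**Impact.** A reader might infer that people with severe liver impairment were in fact treated. Nothing in the documents shows this. Some sites may have applied the background statements anyway. Because dosing has ended, no eligibility change can now protect anyone in this trial.

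**Conclusion.** The inconsistency is real. Two sections say that severe liver impairment is excluded, and 0 of 26 criteria put this into effect, while the three groups named beside it each have a criterion. Following Section 5.5 as written could admit a person whom the protocol says it excludes.

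The size is limited. The number of dosed participants concerned is unknown and may be zero. Post-dosing safeguards reduce the harm but leave eligibility unchanged. Sample size, type I error and the primary comparison are unaffected.

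The conclusion assumes that Section 5.5 is the operative statement of eligibility, as the definition of Eligible and Section 8.1 indicate. It makes no claim about how sites behaved or about what Appendix 1 contains. It is worth correcting because the protocol offers the exclusion as part of its safety case and the correction is cheap.

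**What to change.** **Later versions, or protocols built on this one.** Add to Section 5.5.2 a criterion such as *known diagnosis of severe hepatic impairment*. Assess it by history, as for criterion 16, and have the sponsor's clinicians set the threshold. The cost is one line in the eligibility checklist, with no new test.

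**This trial.** SAP Section 4 records that dosing was discontinued as of 4 February 2021, so what remains is reporting.
- Do not state in the study report that severe liver impairment was excluded by criterion.
- Note any recorded liver disease by arm among dosed participants, from the medical history summary by system organ class and preferred term that SAP 13.1 already plans for the Safety population.
- Give severity only where the recorded term shows it. The summary may not identify severe cases, so the count cannot be read as the number whom the missing criterion would have excluded.

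The cost is one accurate sentence and one count from an output that is already planned.

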## 4. Objectives and Endpoints

Objectives and endpoints are provided in [Table 3](#).

**Table 3: Objectives and Endpoints**

Objectives	Endpoints
Primary	
To characterize safety of study intervention	
Through Day 35
 
 
• Frequencies of grade 3 AEs and grade 4 AEs
 
• AEs resulting in study intervention discontinuation
 
• All SAEs
 

To assess efficacy of study intervention	
 
• Proportion of participants who progress to moderate or severe disease category or higher (Gates MRI ordinal scale <math>\geq 3</math>) through Day 28
 

Secondary	
To assess clinical efficacy of study intervention	
 
• Time to disease resolution, defined as BOTH viral clearance (two consecutive negative diagnostic tests) and symptoms resolution (new onset COVID-19 symptoms resolved, and pre-existing symptoms returned to baseline*) through Day 28
 
• Time to disease resolution, defined as symptoms resolution only (new onset COVID-19 symptoms resolved, and pre-existing symptoms returned to baseline*) through Day 28
 
• Proportion of participants who progress to moderate or severe disease category or higher (Gates MRI ordinal scale <math>\geq 3</math>) at Days 8, 14 and 21
 
• Proportion of participants who achieve disease resolution at Days 8, 14, 21 and 28
 
• Gates MRI scale score at Days 8, 14, 21 and 28
 
• WHO ordinal scale score at Days 8, 14, 21 and 28
 
• Incidence and number of days of hospitalization at Days 8, 14, 21 and 28
 

Exploratory objectives	
To assess virological efficacy	
 
• Quantity (and change from baseline) of SARS-CoV-2 virus at Days 8, 14, 21 and 28
 

To assess viral sequence	
 
• Phylogenetic relationships of SARS-CoV-2 viruses sequenced from positive nasal swab samples
 

\*Baseline refers to health status prior to contracting COVID-19.

